10.2. Study Intervention Compliance

Define how adherence to the protocol (e.g., administration of study intervention, use of device,) will be assessed, and verified (if applicable, e.g., plasma assays, electronic monitoring devices, daily diaries).

Study participants will be monitored daily to confirm if patient has had any dislodgements or has reported any issues with the placement of the securement method. Data will be collected in REDCap.

10.3. Permitted Concomitant Therapy

This section should be consistent with the medication restrictions in the inclusion/exclusion criteria previously listed. Describe how allowed concomitant therapy might affect the outcome (e.g., drug-drug interaction, direct effects on the study endpoints).

N/A

10.4. Rescue Medicine

List all medications, treatments, and/or procedures that may be provided during the study for “rescue therapy” and relevant instructions.

N/A, no rescue medicine

11. Study Intervention Discontinuation

11.1. Discontinuation of Study Intervention

Describe the criteria for discontinuing the study intervention (e.g., halting rules), including any monitoring test(s) and associated clinical decision point(s). Include reasons for temporary discontinuation of the study intervention (e.g., type and quantity of adverse events), clearly stating the length of time, if applicable, and describe the data to be collected at the time of study intervention discontinuation and approaches for restarting administration of or re-challenging with study intervention.

The endpoint of the study is device removal (either intentionally at up to 30 days or inadvertently prior to that time.) If the tube is dislodged prior to end of needing a feeding tube the device will not be used on subsequent insertion/maintenance of the new feeding tube.

11.2. Continued Follow-up Discontinuation of Study Intervention

Describe efforts that will be made to continue follow-up of participants who discontinue the study intervention, but remain in the study for follow-up, especially for safety and efficacy study endpoints (if applicable). Reasonable efforts must be made to undertake protocol-specified safety follow-up procedures to capture adverse events (AE), serious adverse events (SAE), and unanticipated problems involving risks to subjects or others (UPIRSOs).

N/A – no follow up is performed after intervention is complete

12. Statistical Considerations

12.1. Statistical Hypotheses

State the formal and testable null and alternative hypotheses for primary and key secondary endpoints, specifying the type of comparison (e.g., superiority, equivalence or non-inferiority, dose response) and time period for which each endpoint will be analyzed.

Hypothesis: The use of a nasal bridle system will improve retention of nasoenteric feeding tubes in hospitalized children age 0-18 years of age.

Null hypothesis: The use of nasal bridle system will not improve retention of nasoenteric feeding tubes in hospitalized children age 0-18 years of age.

Time point: Analysis for duration of nasoenteric feeding tube requirement or until tube becomes dislodged but no longer than 30 days.

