COVER PAGE FOR PROTOCOL AND STATISTICAL ANALYSIS PLAN

Official Study Title: Improving Retention of Nasoenteric Feeding Tubes in Pediatric Patients Using a Nasal Bridle

NCT number: NCT 04621734

IRB Approval Date: 04/09/2020

Unique Protocol ID: HSC20190225H

Form CT

UTHSA Clinical Trial Description

This form is not mandatory. Other documents are acceptable if equivalent information is provided.

UTHSCSA Tracking Number (internal use only)	HSC20190225H	1. Original Version Date	07/01/2019
		1.1. Revision Date(s) add rows as needed	10/08/19, 04/09/2020

2. Background

Briefly discuss the important literature relevant to the trial and that provides background for the trial. Include the importance of the trial and any relevant treatment issues or controversies.

Nasoenteric feeding tubes are commonly used in the Pediatric ICU as a way to enterally provide nutrition and medication. The traditional method of securing these tubes has been by the use of adhesive tape on the face but unintentional tube dislodgment continues to be a common occurrence. Tube dislodgment leads to delays in nutrition and medication administration, multiple tube replacements, which result in discomfort and extra radiation exposure, and increased consumption of hospital resources with the additional cost of replacement tubes and radiographs. The nasal bridle (BridlePro) is an FDA approved device invented and manufactured by Applied Medical Technology, Inc (AMT) and is an alternative securement method using the structure of the nasal cavity to secure the nasoenteric tube in both adults and children. There have been several studies in the adult population revealing a reduction in dislodgment but only 1 pediatric study, published in 2016, in a very narrow population. This is an investigator-initiated study to compare tube dislodgment rates when the tube is secured with adhesive tape vs the AMT BridlePro device.

3. Objectives and Endpoints *All data points collected in the study should support an objective or have a regulatory purpose.*

Complete the table – add rows as needed.

3.1. Objective(s) Clearly and concisely define the primary and secondary outcomes.	3.2. Endpoint Clearly define the endpoints. (endpoints are the basis for concluding that the objective has been met).	3.3. Justification for Endpoint Briefly explain why the endpoint(s) were chosen.

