Primary outcome: Tube dislodgment rate Secondary outcomes: Time to tube dislodgment, cost of additional feeding tubes and radiographs, number of additional radiographs needed for tube replacement, time of missed nutrition	The endpoint will be when a patient no longer requires a nasoenteric tube because full oral feedings have been met, when a tube is dislodged and successfully replaced, or when the bridle has been in place for 30 days.	When a patient no longer requires a feeding tube, it is standard practice to remove the tube. When a tube is dislodged, the data will be collected for the study and they will have fulfilled the objective and the patient will resume standard treatment. The BridlePro is FDA approved for 30 days of use.

4. Rationale

Briefly state the reason for conducting the clinical trial.

The reason for conducting the investigator initiated clinical trial is to compare the use of a nasal bridle to adhesive tape as a way to secure nasoenteric feeding tubes to improve retention rates.

5. Study Design

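### Sections 3.2, 11.1, 11.2 and 12.1 end observation at different points, and none gives the replacement-radiograph, cost and missed-nutrition endpoints a window that covers them

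*Combined protocol and SAP*

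**What the plan says.** The form's instruction in section 12.1 asks for the "time period for which each endpoint will be analyzed". The plan answers with a single window: "Analysis for duration of nasoenteric feeding tube requirement or until tube becomes dislodged but no longer than 30 days".

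Section 11.1 makes device removal, planned or inadvertent, the endpoint of the study. It adds that after a dislodgment "the device will not be used on subsequent insertion/maintenance of the new feeding tube". Section 11.2 states that "no follow up is performed after intervention is complete".

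Section 3.2 sets a different stop. Apart from the end of tube need, participation ends "when a tube is dislodged and successfully replaced, or when the bridle has been in place for 30 days". Section 3.3 explains: "When a tube is dislodged, the data will be collected for the study and they will have fulfilled the objective"; the child then goes back to standard treatment.

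Sections 3.1 and 12.4 list four secondary endpoints: time to dislodgment, radiographs for replacement, cost of replacement tubes and radiographs, and time of missed nutrition. Section 12.4 gives none of them a window or a method. Section 8.5 says that radiographs for replacement tubes continue as routine care, and section 8.6 lists chart review.

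Among the reasons for the trial, section 2 (Background) gives "multiple tube replacements, which result in discomfort and extra radiation exposure", together with delayed nutrition and the cost of extra tubes and radiographs.

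**The concern.** A radiograph for a replacement tube, the cost of that tube and the feeding time lost all come after the tube has come out. A window that closes at dislodgment closes just before the first of them can occur. The section that runs longer, 3.2, stops at the first successful replacement. That omits any wait before feeding restarts and every later replacement.

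The primary outcome is not affected. What is at stake is whether two data abstractors would collect the same thing for three of the four secondary endpoints, and whether those endpoints can speak to the repeated burden used to justify the trial.

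**Working it through.** **1. The plan's own figures.** The plan states no dislodgment rate, duration of tube need or expected effect. The 30 per arm in section 12.2 comes without inputs and does not bear on this point. There is therefore no figure to reproduce, and the check is first a comparison of texts.

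**2. The stops side by side.**

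| Section | Observation after a dislodgment | Replacement radiographs and cost | Missed nutrition |
|---|---|---|---|
| 12.1 | ends at dislodgment | outside the window | outside the window |
| 11.1 with 11.2 | ends at device removal, no follow-up | outside the window | outside the window |
| 3.2 with 3.3 | ends at successful replacement | first episode only | first episode, up to replacement |

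Section 11.2 does not itself mention dislodgment. The link runs through 11.1, where inadvertent removal is an endpoint. The cap under 3.2 is one successful replacement episode, not one tube or one film, because several attempts may be needed. No section extends observation beyond the first replacement.

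**3. How much a one-episode cap could leave out (illustration).** All inputs are assumptions:
- tape hazard h = 0.03, 0.06 or 0.10 per day, constant over time;
- days of tube need D = 7, 14 or 21;
- bridle hazard ratio HR = 0.3 or 0.5, so the bridle hazard is hb = h × HR;
- tape hazard in both arms after a first loss, because 11.1 does not reuse the bridle.

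Replacements per child, first episode only:
- tape: 1 − exp(−hD)
- bridle: 1 − exp(−hb·D)

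Replacements per child, all episodes:
- tape: hD
- bridle: [1 − exp(−hb·D)] + h·[D − (1 − exp(−hb·D))/hb]

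Share of tape-arm replacements left out = 1 − [1 − exp(−hD)]/(hD):
- lowest case, hD = 0.03 × 7 = 0.21: 1 − 0.189/0.21 = 9.8%
- middle case, hD = 0.06 × 14 = 0.84: 1 − 0.568/0.84 = 32%
- highest case, hD = 0.10 × 21 = 2.1: 1 − 0.878/2.1 = 58%

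Middle case with HR = 0.3, so hb = 0.018 and hb·D = 0.252:
- first episode: tape 0.57, bridle 0.22, difference 0.35
- all episodes: tape 0.84, bridle 0.22 + 0.06 × (14 − 0.2228/0.018) = 0.32, difference 0.52

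The first-episode difference is thus about one third smaller than the all-episode difference. Over all 18 combinations it is about 10-65% smaller. These are two different estimands, so the gap shows how far they part under the assumptions. It is not an error in either one.

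**The case against.** The strongest reply is that this is a deliberate first-tube design. Section 3.3 says that the child has met the objective at dislodgment, and 11.1 returns later tubes to other securement. Stopping at dislodgment is the right window for retention, which is all that the hypotheses in 12.1 address. The Background's remark on repeated replacements is motivation and does not define an endpoint. Counting later tubes would also mix bridle time with post-bridle time in one arm. Much of this stands. It is why first dislodgment should remain the primary event, and why an all-replacement count belongs beside the first-episode result, not in its place. It does not remove the conflict between the stops or supply the missing windows.

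A reader might also infer more than the documents support:

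- **That no data would be collected for these endpoints.** This follows only from a literal 12.1 with 11.1 and 11.2. Section 3.3 says that data are collected at dislodgment, and routine radiographs (8.5) and chart review (8.6) make the first episode observable. The separate Schedule of Activities file (8.7) is not in the text and might bear on timing.
- **That the endpoints are defined as totals of resource use.** Neither 3.1 nor 12.4 says total or cumulative. Section 12.4 even refers to the replacement tube in the singular.
- **That the cost conclusion would be wrong in size.** A cost per first dislodgment is correct for its own question, and the all-replacement benchmark is one estimand among several. If the bridle were in use throughout, the same middle-case inputs would give 0.018 × 14 = 0.25 replacements per child, and a difference of 0.84 − 0.25 = 0.59 instead of 0.52.
- **That the endpoints merely repeat the yes/no primary outcome.** One episode can involve several tubes or films, and missed nutrition is a duration.

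**Conclusion.** The concern holds as a conflict in the text and a gap in coverage. Four sections give stops that do not agree, and the only stated analysis window, taken as written, excludes three of the four secondary endpoints. The likelier reading, to "when a tube is dislodged and successfully replaced", admits one episode per child and leaves the interval from replacement to resumed feeding uncovered. On either reading the trial cannot measure repeated replacement.

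The textual finding needs no assumptions. The 10-58% of tape-arm replacements left out rests entirely on assumed hazards and durations and on a constant hazard; it shows a plausible scale and is not an estimate for this trial. The primary outcome and time to dislodgment are unaffected. The point should be settled before analysis, but it does not threaten the main comparison.

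**What to change.** 1. Keep first dislodgment as the primary event, and keep the first-event window for time to dislodgment.
2. Reconcile 3.2, 11.1, 11.2 and 12.1, and state a window for each secondary endpoint. At the least, let replacement radiographs, replacement cost and missed nutrition run until the replacement tube is confirmed and feeding has resumed.
3. In addition, continue chart review in both arms until tube need ends, discharge, or day 30 from randomisation, whichever comes first. Report all replacements by randomised arm, however later tubes are secured, alongside the first-episode result.

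Items 1 and 2 are wording changes. Item 3 costs a few more days of chart review per child, a procedure already listed in 8.6. It needs no extra visits, procedures or patients and changes no clinical management. Its drawback should be stated in the plan: because 11.1 does not allow reuse of the bridle, all-replacement counts in that arm describe the consequence of starting with a bridle, not of continuous bridle use.

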12.2. Sample Size Determination

Include number of participants to recruit, screen, and enroll to have adequate power to test the key hypotheses for the study. Provide all information needed to validate your calculations and judge the feasibility of enrolling and following the necessary number of participants.

Plan to enroll 30 patients in the study arm and 30 patients in the control arm.

12.3. Populations for Analyses

Clearly identify and describe the analysis datasets (e.g., which participants will be included in each).

Study group: patients with nasoenteric tubes secured using the AMT BridlePro

Control group: patients with nasoenteric tubes secured using adhesive tape

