5.1. Number of Groups/Arms 2 Group name(s) Control arm and study arm			
5.2. Overall Design Select all applicable			
	Randomization		Cluster Randomized
	Group-Sequential		Adaptive Design

	Parallel Design				Placebo-Controlled							
	Superiority				Equivalence					Non-inferiority		
Device			Pilot			Pivotal				Post-Approval		
Drug/Biologic		Phase 1		Phase 1/2		Phase 2		Phase 2/3		Phase 3		Phase 4
 Dose escalation		If yes, details →										
 Dose ranging		If yes, details →										
 Sub-studies		If yes, details →										
5.3. Other Design Details:												

6. Study Population												
6.1. Study Population(s) Label/Name To add more populations – select a row, copy & paste			6.2. Identify the criteria for inclusion The criteria that every potential participant must satisfy, to qualify for study entry. All individuals in this study population must meet all of the inclusion criteria in order to be eligible to participate in the study				6.3. Identify the criteria for exclusion The characteristics that make an individual ineligible for study participation. All individuals in this study population meeting any of the exclusion criteria at baseline will be excluded from study participation.					
Patients who require a nasoenteric feeding tube, admitted at University Hospital, ages 0-18 yo			Need for nasoenteric feeding tube Admitted at University Hospital Age 0-18 yo				Facial trauma, nasal airway obstructions, thrombocytopenia (<100 K/µL), s/p septoplasty, patients with vomer bone graft, nasoenteric feeding tube placed and secured prior to being screened for study, contraindication for the use of the BRIDLEPro Does not meet inclusion criteria					
6.4. Will screen failures be allowed to re-screen at a later date?				No		Yes	If yes, describe criteria below ↓					

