8.2. Devices

Nasoenteric feeding tube will be placed by the bedside nurse as part of routine care. AMT BridlePro will be placed by trained nurses for patients on the study arm of the trial.

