9.1. Acquisition and accountability

State how the study intervention and control product will be provided to the investigator. Describe plans about how and by whom the study intervention will be distributed, including participation of a drug repository or pharmacy, and plans for disposal of expired or return of unused product.

AMT representative will provide in-person training for the nurses and providers placing the BridlePro and will provide the nasal bridles as per the clinical trial material transfer agreement. The nasoenteric tubes that will be used in the control and study arm are the standard tubes used in the unit and adhesive tape that is used for securing tubes in the control group.

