9.4. Preparation

Describe the preparation of the study intervention and control product, including any preparation required by study staff and/or study participants. Include thawing, diluting, mixing, and reconstitution/preparation instructions in this section. For devices, include any relevant assembly or use instructions.

Device assembly of the BridlePro system per package instructions and training provided by AMT representative.

10. Study Intervention Additional Details**10.1. Measures to Minimize Bias: Randomization and Blinding**

This section should contain a description of randomization and blinding procedures (if applicable to the study design). It should include a description or a table that describes how study participants will be assigned to study groups, without being so specific that blinding or randomization might be compromised. Plans for the maintenance of trial randomization codes and appropriate blinding for the study should be discussed. The timing and procedures for planned and unplanned breaking of randomization codes should be included. Include a statement regarding when unblinding may occur and who may unblind. Provide the criteria for breaking the study blind or participant code. Discuss the circumstances in which the blind would be broken for an individual or for all participants (e.g., for serious adverse events (SAEs)). Indicate to whom the intentional and unintentional breaking of the blind should be reported.

Study participants will be randomized to the control or study arm using REDCap Randomization Module. Sealed envelopes will be locked in the PICU/PCCU where nasogastric tubes and bridles will be stored. When a patient meets criteria for the study, the study administrator will be notified, an envelope will be drawn to randomize the participant into one of the two groups and patient

information will be recorded in a log stored on a password protected UH computer share drive.

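### Section 12.3 describes the analysis groups by the securement used, and nothing in the plan says that children are analysed as randomised or how a child not secured as allocated is counted

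*Combined protocol and SAP*

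**What the plan says.** Section 12.3, where the form asks which participants enter each dataset, has two lines: "Study group: patients with nasoenteric tubes secured using the AMT BridlePro" and "Control group: patients with nasoenteric tubes secured using adhesive tape". Section 12.4 lists endpoints and names no test, model or analysis set.

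Elsewhere the plan speaks of arms. Section 10.1 says that "an envelope will be drawn to randomize the participant into one of the two groups". Section 8.2 says "AMT BridlePro will be placed by trained nurses for patients on the study arm of the trial". Section 9.1 mentions "adhesive tape that is used for securing tubes in the control group". Section 12.2 plans 30 children in each arm.

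The exclusions in Section 6.3 remove some likely failures of bridle placement, among them any "contraindication for the use of the BRIDLEPro". Section 10.2 has a daily check entered in REDCap ("Study participants will be monitored daily to confirm if patient has had any dislodgements"), which also covers problems with the securement, but it gives no counting rule.

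The follow-up wording is mixed:
- **Section 3.2.** Two endpoints concern the tube ("when a patient no longer requires a nasoenteric tube because full oral feedings have been met, when a tube is dislodged and successfully replaced"). The third is reached after 30 days of bridle placement.
- **Section 11.1.** The study ends when the device comes out.
- **Section 11.2.** No one is followed once the intervention is over.
- **Section 12.1.** The analysis period fits both arms: as long as a tube is needed or until it dislodges, with a 30-day ceiling.

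**The concern.** Randomisation protects the comparison only if children stay in the arm they were drawn into. If Section 12.3 is applied as worded, a child allocated to the bridle but secured with tape moves to the control group. Should such children be more prone to dislodgment than the rest, the bridle group loses its high-risk members and the tape group gains them, so the bridle looks better than it is. If they are less prone, the bias runs the other way.

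If the wording is only shorthand, a gap remains, because there is still no rule for a departing child. No blinding is described, so the choice could be made by people who know both securement and outcome.

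**Working it through.** **Text check.** The whole document was searched for an as-randomised, intention-to-treat, per-protocol or as-treated statement, and for a rule on failed, absent or switched securement. There is none.

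**Inputs from the plan.** 30 children per arm (Section 12.2). No basis is given for this number, so there is no figure of the plan's own to reproduce.

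**Assumed inputs.** No true effect; base dislodgment risk p = 30% or 40%; k of 30 bridle-arm children taped from the start, with risk r; two-sided 5% level; pooled z test or Fisher's exact test.

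**Model.** The remaining 30 - k bridle-arm children have risk p0 = (30p - kr)/(30 - k), so both randomised arms have mean risk p.
- As randomised, the expected difference is p - p = 0.
- As secured, it is (30p + kr)/(30 + k) - (30p - kr)/(30 - k), tape minus bridle.

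**Example, p = 0.30, r = 0.70, k = 3.** Bridle: (9 - 2.1)/27 = 0.256. Tape: (9 + 2.1)/33 = 0.336. The spurious benefit is 8.1 points. Exact enumeration gives type I error of 10.4% (pooled z) or 7.7% (Fisher) as secured, against 4.4% or 2.3% as randomised.

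**Departing children at higher risk (r = 50% or 70%), as secured**

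| Departing | Spurious benefit, points | Type I error, pooled z | Type I error, Fisher |
|---|---|---|---|
| 0 of 30 | 0 | 4.9% | 2.6% |
| 1 of 30 | 0.7-2.7 | 5.1-5.4% | 3.4-3.9% |
| 3 of 30 | 2.0-8.1 | 5.3-10.4% | 3.8-7.7% |
| 6 of 30 | 4.2-16.7 | 6.1-27.9% | 4.2-21.5% |

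The last row marks an outer case; nothing in the plan points to so many departures.

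**Departing children at lower risk (r = 10% or 20%), 3 of 30.** The bias is 2.0-6.1 points against the bridle, with type I error of 5.0-7.5% (pooled z) or 3.8-5.5% (Fisher). If r = p, the bias is 0.

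**Analysed as randomised.** The same scenarios give bias 0 and type I error of 3.8-4.9% (pooled z) or 1.9-2.6% (Fisher).

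**If the bridle works.** Assume a risk ratio of 0.4 in children who receive it, p = 0.30, k = 3 and r = 50-70%.
- Every bridle placed: 0.6 × 0.30 = 18.0 points.
- As randomised: 0.6(p - kr/30), which is 0.6 × 0.25 = 15.0 points at r = 50% and 0.6 × 0.23 = 13.8 at r = 70%.
- As secured: (30p + kr)/(30 + k) - 0.4(30p - kr)/(30 - k) = 20.7-23.4 points, above even the all-placed value.

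**The case against.** The strongest reply is that Section 12.3 merely names the two arms. Sections 8.2, 9.1, 10.1 and 12.2 all use arm language, and that reading is plausible. A reader might infer that the investigators intend an as-treated analysis; the documents do not establish that. What stands is that neither reading yields a rule for a child not secured as allocated.

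Departures may also be few. Section 6.3 excludes facial trauma, nasal airway obstruction, low platelets, tubes secured before screening and any contraindication to the bridle. No rate is given, and the largest figures need 6 departures or a 70% risk. With one departure, type I error is at most 5.4% (pooled z) or 3.9% (Fisher). These rates also depend on a test chosen for this check, since the plan names none. All of this stands and limits the weight of the point. Against it, Section 7 allows no extra sedation for securement and Section 8.2 relies on trained nurses, so some bridles may not be placed. That is inference, not a stated fact.

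The model covers only bridle-arm children taped from the start. It has no later switch and no tape-to-bridle departure.

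Section 10.2 already collects securement problems daily, so recording departures adds less than it might seem.

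**Conclusion.** The point holds as a gap that should be fixed before analysis. Section 12.3 groups children by securement used, and nothing in the plan overrides that or covers departures. Applied literally, it gives an as-treated comparison.

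The size is conditional on the assumptions above: a point or two for one higher-risk departure and 2.0-8.1 points for three.

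Two stronger readings are not supported. One is that the result will favour the bridle: the direction depends on the risk of the departing children, and with no departures, or departures unrelated to risk, the bias is zero. The other is that the existing endpoints already serve every child whatever the securement. Section 12.1 does, but the third endpoint in Section 3.2 and the end of study in Section 11.1 are tied to the bridle. Section 11.2 also leaves open whether a child whose bridle is removed early and whose tube is then taped is still observed. An as-randomised analysis needs that child's outcome. Confidence is medium, because shorthand is a fair reading and the departure rate is unknown.

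**What to change.** Replace the text of Section 12.3 with: *Primary analysis: all randomised children in whom a nasoenteric tube is placed, analysed in the arm to which they were randomised, whatever securement was used.* Then:

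- Report randomised children who never have a tube placed, by arm and with the reason. Leaving them out is a choice: it is an exclusion after randomisation that could depend on arm, as no blinding is described. Add a sensitivity analysis that counts them as having no dislodgment. Each such child changes that arm's rate by p - 29p/30, which is 1.0 point at p = 0.30 and 1.3 at p = 0.40.
- Keep the as-secured comparison as a labelled sensitivity analysis.
- Add a field for departure from allocation and its reason to the daily REDCap check in Section 10.2.
- Reconcile the bridle-specific wording in Sections 3.2 and 11.1, and the no-follow-up statement in Section 11.2, with the arm-neutral period in Section 12.1. Outcome data should then be collected over that period for every randomised child with a tube, including one whose securement changes.

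**Cost.** Wording in four sections, one REDCap field, and outcome collection to the end of the Section 12.1 period for any child whose securement changes; no extra children. The as-randomised estimate includes failed placements, so it is smaller and has less power. With an assumed risk ratio of 0.4 and 3 of 30 departing at 50-70% risk, pooled-z power is 22-27% against 40% with no departures at base risk 30%, and 38-43% against 55% at base risk 40%.
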